	divided by a pre-determined period following treatment initiation (e.g., 6 and 12 months) Adherence will be described as a continuous variable and as a binary variable (<0.80: non-adherent, ≥ 0.80 : adherent)
Treatment persistence	Persistence to relugolix will be described as the proportion of patients who did not discontinue relugolix (i.e., with a treatment gap, switch to another ADT, or death; the minimum days of treatment gap, e.g., 45 or 60 days, will be finalized based on sample size and clinical input) during the follow-up period. Treatment gaps will be assessed from the end of the days of supply of the previous prescription to the earliest of the next prescription or the end of data availability.
PSA response	Only if sample size is sufficient and among patients with at least one baseline and one follow-up period PSA measure: 
• The number and percentage of patients with $\geq 50\%$ and $\geq 90\%$ decline from the baseline PSA to any PSA measurement during the follow-up period and while on relugolix• The number and percentage of patients with the nadir PSA value during the follow-up period and on treatment of relugolix < 0.01, 0.1, and 0.2 ng/mL
Testosterone response	Only if sample size is sufficient and among patients with at least one follow-up period testosterone measure: 
• The number and percentage of patients with at least one testosterone value of <50ng/dL and <20 ng/dL during the follow-up period and while on relugolix 
If sample size is sufficient, the analysis above may be conducted among patients with at least one baseline and one follow-up period testosterone measure

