9.7.2.3. Time to treatment changes

Kaplan-Meier analysis will be conducted to describe the following time-to-event outcomes for the treatment patterns as listed in [Table 3](#):

PFIZER CONFIDENTIAL

- Time to discontinuation of relugolix
- Time to switching to a different ADT treatment
- Time to add a new systemic PC treatment to relugolix

The number and proportion of patients with the corresponding event will be plotted over time and the number at risk table over time will be presented. The median time to event will be calculated.

9.7.3. Data analysis for Objective 3: To estimate adherence and persistence with relugolix among patients with PC who initiated relugolix

Adherence to relugolix as defined in [Table 3](#) will be described. MPR will be summarized over the entire exposure to relugolix during the follow-up period. PDC will be summarized within the 6, 12, and 18 months (tentatively, pending on the final length of follow-up) since the index date. Means, standard deviations, medians, and interquartile range will be estimated for adherence as a continuous variable. Counts and percentages will be estimated for adherence as a binary variable. Patients will be required to have complete follow-up data during the time to be included in each adherence calculation.

Persistence to relugolix as defined in [Table 3](#) will be described using Kaplan-Meier analysis since the index date. The number and proportion of patients persistent to relugolix will be plotted over time and the number at risk table over time will be presented.

9.7.4. Data analysis for Objective 4: To assess testosterone suppression and PSA responses among ADT naïve patients with PC who initiated relugolix

If sample size is sufficient, the count and percentage of patients with testosterone responses as defined in [Table 3](#) will be calculated among ADT naïve patients with at least one testosterone measure during the follow-up period. Similarly, if sample size is sufficient, the count and percentage of patients with PSA responses as defined in [Table 3](#) will be calculated among ADT naïve patients with at least one baseline and one follow-up period PSA measure.

9.7.5. Data analysis for Objective 5: To describe and compare demographics and clinical characteristics between Black and non-Hispanic White patients with PC who initiated relugolix

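### PSA and testosterone response counts only values taken on relugolix, but the denominator accepts any follow-up value, so patients tested only after stopping cannot respond while untested patients are left out

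*Combined protocol and SAP*

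**What the plan says.** Section 9.3, Table 3, defines the response endpoints for Objective 4. A PSA decline of at least 50% or 90% is judged from baseline "to any PSA measurement during the follow-up period and while on relugolix". The nadir thresholds (0.01, 0.1 and 0.2 ng/mL) apply to "the nadir PSA value during the follow-up period and on treatment of relugolix". Testosterone below 50 or 20 ng/dL carries the same on-relugolix limit.

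The groups over which the percentages are taken carry no such limit. PSA response is assessed "among patients with at least one baseline and one follow-up period PSA measure" and testosterone response "among patients with at least one follow-up period testosterone measure". Section 9.7.4 keeps these groups and adds only the ADT naïve restriction; for testosterone the count is made "among ADT naïve patients with at least one testosterone measure during the follow-up period".

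Under sections 9.1 and 9.2.1, follow-up runs from the index date to death, end of eligibility or end of data. Two of the four treatment patterns in Table 3 are discontinuations observed within that period.

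The persistence row of Table 3 treats a patient as having discontinued "with a treatment gap, switch to another ADT, or death". It sets the start of a gap: "Treatment gaps will be assessed from the end of the days of supply of the previous prescription". It leaves the length open: "the minimum days of treatment gap, e.g., 45 or 60 days, will be finalized based on sample size and clinical input". The response rows do not refer to this definition. Table 2 allows the baseline PSA and testosterone values to be taken on the index date itself.

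**The concern.** Numerator and denominator use different time windows. A patient whose only follow-up values come after stopping or switching enters the denominator, cannot meet any response criterion and has no on-treatment nadir. A patient with no follow-up value is excluded. Both lack an on-treatment value, yet they are handled in opposite ways.

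The resulting percentage describes neither all ADT naïve initiators nor those evaluable on treatment. It mixes response with the timing of tests, and the planned output does not include the count that would let a reader separate the two. These are the plan's only measures of treatment response.

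**Working it through.** The plan gives no expected response rate, sample size or testing frequency, so there is no figure to reproduce. What can be checked is how the definitions interact.

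**1. The windows side by side (Table 3 and 9.7.4)**

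| Endpoint | Value that can count as a response | Value that admits a patient to the denominator |
|---|---|---|
| PSA decline | in follow-up and on relugolix | a baseline value, and any in follow-up |
| PSA nadir | in follow-up and on relugolix | a baseline value, and any in follow-up |
| Testosterone | in follow-up and on relugolix | any in follow-up |

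The optional testosterone analysis that also requires a baseline value has the same mismatch.

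**2. Effect of patients with only off-treatment values**

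Let N be the denominator as written, m the patients in it with only off-treatment values, x the responders, and q = m/N.

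- Rate as written: x/N.
- Rate among patients with an on-treatment value: r = x/(N − m).
- Ratio: (N − m)/N = 1 − q, so the rate as written is r × (1 − q).
- Absolute reduction: r × q, which cannot exceed q because r ≤ 1.

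The effect is downward or nil. Each 1% of the denominator with only off-treatment values costs at most 1 percentage point. Assumed figures, N = 100 and m = 5:

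| x | x/100 | x/95 | Difference (points) |
|---|---|---|---|
| 57 | 57.0% | 60.0% | 3.0 |
| 72 | 72.0% | 75.8% | 3.8 |
| 90 | 90.0% | 94.7% | 4.7 |

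**3. Tested only off treatment against never tested**

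Assume 100 ADT naïve patients: 70 with an on-treatment value, of whom 63 respond; 10 tested only after stopping; 20 never tested.

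- As written: 63/80 = 78.8%.
- On-treatment evaluable: 63/70 = 90.0%.
- All initiators, untested counted as non-responders: 63/100 = 63.0%.

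Here q = 10/80 = 12.5%, and 90.0% × 0.875 = 78.8%, as in step 2.

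**4. Can such patients exist?**

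Take a patient with the minimum two prescriptions, assumed to be consecutive 30-day fills (section 9.9 speaks of a first and a second month). Off-treatment days are max(0, F − 60 − g), where F is days of follow-up and g is 0 if treatment ends at end of supply, or 45 or 60 if it ends after the permitted gap.

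| F | g = 0 | g = 45 | g = 60 |
|---|---|---|---|
| 60 | 0 | 0 | 0 |
| 90 | 30 | 0 | 0 |
| 365 | 305 | 260 | 245 |

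Such a patient is off-treatment-only if untested in the first 60, 105 (60 + 45) or 120 (60 + 60) days and tested later. For a patient who switches ADT, on-treatment time ends no later than the switch. The table shows that the case is possible and depends on an unstated rule. It does not estimate q.

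**5. Values on the index date**

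Baseline may fall on the index date (Table 2) and follow-up starts on that date (9.1), so one index-date value could serve as both. A patient with no other follow-up value may then be in the denominator as written without being off-treatment-only. For PSA decline that patient shows no change by construction. An evaluable set that requires a value after the index date removes these patients too, so r × (1 − q) describes only the off-treatment-only part of the change.

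**The case against.** The strongest reply is that the plan never says a patient without an on-treatment value is a non-responder. For the nadir such a patient has no value at all, and an analyst might set them aside as non-evaluable. That is fair: failure follows from applying the two definitions literally, not from a stated rule. But then two analysts could report different percentages from the same text, and a reader could not tell which rule was used.

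The wide denominator might also be a deliberate, conservative choice. The plan does not say so, and the definition does not fit that aim: if stopping were meant to count as failure, patients who stop and are never tested would be kept, and they are dropped.

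A restricted denominator is itself selected, and an any-value response still depends on how often and how long patients are tested on treatment. This stands, and it is why the counts of excluded patients matter as much as the choice of denominator.

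q may be small, because the on-treatment window opens at index and entry requires two prescriptions. This also stands.

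A reader might infer that section 9.7.3 sets a precedent by matching the adherence denominator to its window. It does not. That rule requires complete observation over the period; patients who stop relugolix stay in the PDC calculation, and their uncovered days count against them. It says nothing about an on-treatment condition.

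**Conclusion.** The mismatch is present in both Table 3 and section 9.7.4, affects both endpoints, and is not resolved elsewhere in the document. Relative to patients with an on-treatment value, the literal percentage is lower by the fraction q, or by r × q in absolute terms. This rests on the definitions alone and assumes they are applied as written.

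A reader might infer that the reported response will be materially understated. The documents do not support that: they give neither q, nor r, nor a testing frequency, and the percentages and day counts above are illustrations.

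Impact is minor to moderate. Objective 4 is exploratory, has no hypothesis (9.5), reports counts and percentages only, and runs only if the sample is sufficient. The primary objective and the race comparisons are unaffected.

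**What to change.** In Table 3 and section 9.7.4:

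- Define the evaluable set as ADT naïve patients with at least one value after the index date taken while on relugolix, plus a baseline value for PSA.
- State that an index-date value counts as baseline only.
- Use one rule for the end of on-treatment time in both numerator and denominator, tied to the discontinuation definition in the persistence row, and say whether that time ends at end of supply or after the permitted gap.
- Report, for each endpoint, the numbers of ADT naïve patients tested only off treatment, with only an index-date value, and never tested.
- Add a sensitivity percentage that keeps off-treatment-only patients in the denominator as non-responders.

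The cost is a wording change, three counts and one extra percentage per criterion, from fill and laboratory dates the study already needs. The denominator becomes smaller, by the fraction q plus any patients with only an index-date value. The rate then applies only to patients tested on treatment, and may exceed the rate among all initiators if early stoppers respond less often. The sensitivity percentage shows how much the handling of off-treatment-only patients matters.

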Comorbidities	A binary variable (yes/no) will be created for patients with a diagnosis of each of the following comorbidities during the baseline period: 
• Hypertension• Hyperlipidemia• Diabetes• Urinary tract infection• Chronic obstructive pulmonary disease• Arrhythmia• Congestive heart failure• Myocardial infarction• Stroke• Angina pectoris• Inflammatory bowel disease• Acute coronary syndrome• Sexual dysfunction• Depression• Anxiety• Hot flashes• Cognitive impairment• Major adverse cardiovascula event (defined by any evidence of cardiomyopathy, heart failure, ischemic heart disease, myocardial infarction, pulmonary embolism, or stroke)
PSA	Baseline PSA value (among available) based on the PSA value closest to the index date during the 90-day window (or 180-day, to be finalized based on the number of patients with non-missing PSA value in these time frames) on or prior to the index date will be evaluated.
Testosterone	Baseline testosterone value (among available) based on testosterone value closest to the index date during the 90-day window (or 180-day; will be consistent with the time window for baseline PSA) on or prior to the index date will be evaluated.
Metastatic vs. non-metastatic PC	A binary variable for patients with metastatic vs. non-metastatic PC will be created. Metastatic PC will be

Variable	Operational definition
	defined as having evidence of metastasis during the baseline period or within 90 days since the index date.
ADT naïve vs. ADT experienced	A binary variable for patients who were ADT naïve vs. ADT experienced will be created. ADT naïve will be defined as having no records of any systemic ADT treatment ever based on all available data prior to the index date (i.e., including baseline period data and any available data prior to the baseline period). Systemic ADT treatment includes LHRH agonists and GnRH antagonists (i.e., degarelix, relugolix, goserelin, histrelin, leuprolide, triptorelin)

Table 3. Treatment patterns, adherence, persistence, and clinical variables during the follow-up period

Variable	Operational definition

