Index treatment	
Index treatment regimens include:
 
 • Relugolix monotherapy • Relugolix + NSAA only (at least 90 days of NSAA use) • Relugolix + ARPI +/- NSAA (no chemotherapy) • Relugolix + ARPI + chemotherapy • Relugolix + chemotherapy +/- NSAA (no ARPI) • Relugolix + other (no ARPI, no chemotherapy) 
Index treatment regimen will be defined based on treatments received within 30 days before the index date and within 90 days after the index date.
 
Specific treatments included in each treatment category (i.e., ADT, NSAA, ARPI, chemotherapy, immunotherapy) are described in “Treatment history” in Table 2. Other treatments include immunotherapy, radium 223, olaparib, rucaparib, talazoparib, niraparib and lutetium Lu 177 vipivotide tetraxetan.
 
Number of patients who received any radiotherapy during the index treatment will be summarized.

Variable	Operational definition
Treatment patterns of relugolix	
Treatment patterns of relugolix include:
 
• Continued relugolix as in the index treatment (regardless of discontinuation of concomitant medications)• Continued relugolix with a new add-on systemic PC treatment (excluding ADT)• Discontinued relugolix and switched to another ADT treatment• Discontinued relugolix without switching to another ADT treatment 
Add-on systemic PC treatments include:
 
• ARPI• NSAA• Chemotherapy• Immunotherapy• Radium 223• Ketoconazole• Olaparib• Rucaparib• Talazoparib• Niraparib• Lutetium Lu 177 vipivotide tetraxetan 
Add-on therapy will be evaluated from 90 days after the index period to the end of the follow-up period.

Time to treatment changes	The time to treatment changes of interest include: 
• Time to discontinuation of relugolix• Time to switching to a different ADT treatment• Time to add a new systemic PC treatment to relugolix
Treatment adherence	Adherence to relugolix post the index date will be described using both MPR and PDC: 
• MPR: Sum of the days of supply divided by the number of days between the first fill and the end of the last refill (i.e., including the days of supply from the last refill)• PDC: Sum of the non-overlapping (i.e., not double counting of overlaps) days of supply covered

Variable	Operational definition

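### PSA response counts any on-relugolix value, including values after a new drug is added, and pools all six index regimens into one percentage

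*Combined protocol and SAP*

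**What the plan says.** Table 3 in section 9.3 defines the two response outcomes.

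- **PSA decline:** a fall of at least 50% or 90%, taken as a "decline from the baseline PSA to any PSA measurement during the follow-up period and while on relugolix".
- **PSA nadir:** the number and percentage of "patients with the nadir PSA value during the follow-up period and on treatment of relugolix" below 0.01, 0.1 and 0.2 ng/mL.
- **Testosterone:** "at least one testosterone value of <50ng/dL and <20 ng/dL during the follow-up period and while on relugolix". No baseline value is needed. If numbers allow, "the analysis above may be conducted among patients with at least one baseline and one follow-up period testosterone measure", but that baseline need not be above the castrate range.

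The same table makes continuing relugolix with a newly added systemic prostate cancer drug one of its four treatment patterns. The add-on list includes ARPI, NSAA, chemotherapy, radium 223, PARP inhibitors and lutetium. Such time is therefore on-relugolix time. Table 3 also derives six index regimens, from monotherapy to relugolix with ARPI and chemotherapy, using treatments from 30 days before to 90 days after the index date.

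Section 9.7.4 restricts both outcomes to ADT-naïve men. Testosterone response "will be calculated among ADT naïve patients with at least one testosterone measure during the follow-up period"; PSA response needs one baseline and one follow-up measure. Neither is split by index regimen or cut at an add-on. Table 2 defines ADT naïve as no record, in all available earlier data, of a listed LHRH agonist or GnRH antagonist.

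**The concern.** The on-relugolix limit and the ADT-naïve restriction keep earlier and later ADT out of the response figures. They leave concurrent active treatment in. A man whose PSA first falls by 90% after docetaxel or an ARPI is added is counted in the same way as a man who responded to relugolix alone. A man who started relugolix and an ARPI together enters the same percentage as a man on monotherapy.

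This matters because the rationale (section 7) says the study is to show how relugolix is used, including alone or in combination, and potentially the response to treatment. One pooled figure cannot connect the two. The limitations in section 9.9 say in general terms that treatment-pattern definitions rest on assumptions, but do not warn that the response percentages mix regimens. A reader of the final report could quote the figure as the response to relugolix.

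**Working it through.** The documents state no expected response rate, add-on frequency, regimen mix or sample size. There is no plan figure to reproduce, and every numerical input below is an assumption.

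**1. Direction of the add-on rule (no assumption on rates).** Fix the denominator. The on-relugolix values before an add-on are a subset of all on-relugolix values. Anyone who meets a threshold at some value in the subset also meets it in the full set, so the any-value rate and the nadir rate are each at least as high as the rate cut at add-on.

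**2. Size of the add-on rule.** Let p be the response rate before any add-on, a the share given an add-on while on relugolix, and q the share of non-responders with an add-on who then respond. If add-ons are equally likely in responders and non-responders, the rise is (1 − p) × a × q.

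- p = 0.90, a = 0.05, q = 0.5: 0.10 × 0.05 × 0.5 = 0.0025, or 0.25 points.
- p = 0.50, a = 0.15, q = 0.5: 0.50 × 0.15 × 0.5 = 0.0375, or 3.75 points.

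If add-ons are commoner (15% to 25% of men) and 70% of recipients are non-responders, with p = 0.60 and half of those then responding:

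- 0.15 × 0.70 × 0.50 = 0.0525, so 60% is reported as 65.3%.
- 0.25 × 0.70 × 0.50 = 0.0875, so 60% is reported as 68.8%.

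This second set is the upper end. It implies that 0.105/0.40 = 26% to 0.175/0.40 = 44% of all non-responders receive an add-on. Required follow-up is only 90 days, and add-ons are assessed only from 90 days onwards.

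**3. Pooling.** Let s be the share on combination regimens, t their response rate, and m = p + (1 − p) × a × q the any-value rate on monotherapy. The pooled rate is s × t + (1 − s) × m. With s = 0.20 to 0.50, t = 0.90 to 0.95, a = 0.05 to 0.15 and q = 0.5:

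| p (monotherapy, before add-on) | Lowest pooled rate | Highest pooled rate |
|---|---|---|
| 0.50 | 0.20 × 0.90 + 0.80 × 0.5125 = 0.590 | 0.50 × 0.95 + 0.50 × 0.5375 = 0.744 |
| 0.70 | 0.20 × 0.90 + 0.80 × 0.7075 = 0.746 | 0.50 × 0.95 + 0.50 × 0.7225 = 0.836 |
| 0.90 | 0.50 × 0.90 + 0.50 × 0.9025 = 0.901 | 0.50 × 0.95 + 0.50 × 0.9075 = 0.929 |

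The difference from p splits into (m − p), the add-on part, and s × (t − m), the pooling part. In the top right cell these are 3.75 points and 0.50 × (0.95 − 0.5375) = 20.6 points, together 24.4. The pooling part takes the sign of t − m. With p = 0.90, a = 0.15, s = 0.50 and t = 0.90 it is 0.50 × (0.90 − 0.9075), or −0.4 points. The mostly positive results follow from assuming that combinations respond at 90% to 95%, which the documents do not say.

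**4. Testosterone.** If a share k of men labelled ADT naïve is already castrate at index and the true rate in the others is r, the reported rate is k + (1 − k) × r, a rise of k × (1 − r). With k = 0.10, the rise is 0.10 × 0.30 = 3 points at r = 0.70 and 0.10 × 0.05 = 0.5 points at r = 0.95. With k = 0 it is zero.

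**The case against.** The strongest reply is that the plan claims nothing about relugolix alone. Objective 4 is exploratory, descriptive, run only if numbers suffice, and concerns men who initiated relugolix. The on-relugolix condition is an exposure window, and a pooled percentage is a correct description of pooled initiators. This stands against any charge of a false causal claim, and it limits the severity. It does not answer the point that a rate over monotherapy, combinations and post-add-on time describes none of them.

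Two stronger readings are tempting, and the documents support neither.

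- **That every feature of the definition inflates the rates.** Pooling has no fixed direction: men on combinations may have disease that responds less. A partner drug may start up to 30 days before index, while baseline PSA is the value closest to index, so an already lowered baseline makes a 50% or 90% fall harder to reach. The denominator asks only for a follow-up PSA, not one on relugolix, so read literally a man measured only after stopping is a non-responder.
- **That an added ARPI or chemotherapy inflates testosterone response.** Nothing in the documents shows that these drugs bring testosterone below 50 ng/dL. The ADT-naïve restriction and the exclusion of surgical castration should also remove most castrate baselines. What remains is ADT not recorded in the VA data, and earlier hormonal agents outside the ADT list; neither frequency is given.

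Nor do the documents record why drugs are added, so an add-on cannot be read as proof that the index regimen was failing.

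**Conclusion.** The point holds for PSA. Relative to the index regimen and with a fixed denominator, counting post-add-on values can only raise the response rate. On assumed inputs the rise is about 0.25 to 9 points, the upper end needing frequent add-ons concentrated in non-responders. Pooling the six regimens may add more or pull the other way. If combinations respond at 90% to 95%, a monotherapy rate of 50% before add-on would appear as 59% to 74%, and one of 90% as 90% to 93%. The true size cannot be known from the documents.

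For testosterone, only a small gap remains: about 0 to 3 points if up to 10% of men labelled ADT naïve are already castrate and the true rate is 70% to 95%. This justifies a secondary display and no more. Severity is low to moderate.

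**What to change.** In Table 3 and section 9.7.4:

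- **(a)** Count PSA values only up to the earlier of relugolix discontinuation and the start of a new add-on systemic treatment. Keep the current rule as a sensitivity analysis, with the same stated denominator, so that the difference reflects the cut-off alone.
- **(b)** Report PSA and testosterone responses by index regimen where numbers allow, at least monotherapy against relugolix with ARPI and/or chemotherapy. Label any pooled figure as response on relugolix-containing treatment.
- **(c)** As a secondary display only, show testosterone suppression among men with a measured baseline of at least 50 ng/dL. It should not replace the main set, because the plan already expects missing baselines and the number available is unknown.

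Index regimen, time to add-on and baseline testosterone are already planned variables, so the change is one of wording and tables. The cost is smaller denominators in the strata and the baseline subset, and slightly lower PSA response percentages.

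### Objective 4 counts men already below a testosterone or PSA cut-off before relugolix as responders, because its absolute-threshold endpoints require no baseline level

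*Combined protocol and SAP*

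**What the plan says.** Section 9.3, Table 3 defines the responses and Section 9.7.4 says how they are tabulated.

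- **PSA nadir.** The count and percentage of "patients with the nadir PSA value during the follow-up period and on treatment of relugolix < 0.01, 0.1, and 0.2 ng/mL". The denominator is "among patients with at least one baseline and one follow-up period PSA measure", so a baseline value must exist, but no minimum is set.
- **PSA decline.** At least 50% and at least 90% "decline from the baseline PSA to any PSA measurement during the follow-up period and while on relugolix".
- **Testosterone.** "at least one testosterone value of <50ng/dL and <20 ng/dL during the follow-up period and while on relugolix". Section 9.7.4 uses the denominator "among ADT naïve patients with at least one testosterone measure during the follow-up period", with no baseline value needed. Table 3 adds an optional analysis in men who also have a baseline testosterone, without saying what that value must be.
- **ADT naïve** (Table 2). "ADT naïve will be defined as having no records of any systemic ADT treatment ever based on all available data prior to the index date". The drugs that count are LHRH agonists and GnRH antagonists.
- **Baseline PSA and testosterone** (Table 2). The value closest to the index date in the 90 (or 180) days up to and including it. Both are described; neither decides who can be a responder.

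**The concern.** The objective is to assess testosterone suppression and PSA response in ADT-naïve men who start relugolix. A fixed cut-off measures response only in men who start on the other side of it.

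Two routes let men in who do not:

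- **Unrecorded ADT.** The data source covers encounters within the VA from 2006, and no linkage to outside care is described. A man injected elsewhere who arrives with testosterone of, say, 15 ng/dL is classed as naïve and then counted as suppressed at both cut-offs.
- **Low PSA for other reasons.** This route does not depend on missed ADT. Prostatectomy, radiotherapy, ARPI and NSAA are listed as treatment history, but none affects naïve status. A man with PSA of 0.05 ng/mL after prostatectomy meets the 0.2 and 0.1 ng/mL cut-offs if he does not change at all. In addition, the index regimen may include drugs given up to 30 days before the index date, while baseline PSA is the value closest to that date, so it can be taken after those drugs were started.

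At stake is the meaning of the reported percentages. They would mix response with starting position and be read as response.

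**Working it through.** The plan states no expected response rate, sample size or power for Objective 4, so there is no figure to reproduce. The check has two parts.

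**1. Does each endpoint require a starting level?**

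| Endpoint | Baseline value required? | Baseline level required? | Can no change count as response? |
|---|---|---|---|
| Testosterone <50, <20 ng/dL (main) | No | No | Yes |
| Testosterone, optional analysis | Yes | No | Yes |
| PSA nadir <0.2, <0.1, <0.01 ng/mL | Yes | No | Yes |
| PSA decline ≥50%, ≥90% | Yes | No | No, it is relative to the man's own baseline |

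The gap therefore lies in the absolute-threshold endpoints.

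**2. How large could the effect be?** For one cut-off, let

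- q = share of the denominator already below it at baseline, assumed to have an on-treatment value below it too;
- r = rate among men at or above it at baseline, which is the quantity of interest.

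Reported rate = q + (1−q)r. Excess over r = q + (1−q)r − r = q(1−r).

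Neither q nor r is in the documents. Over assumed ranges:

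| r | Excess at q = 5% | Excess at q = 15% | Reported rate |
|---|---|---|---|
| 50% | 0.05 × 0.50 = 2.5 points | 0.15 × 0.50 = 7.5 points | 52.5–57.5% |
| 70% | 0.05 × 0.30 = 1.5 points | 0.15 × 0.30 = 4.5 points | 71.5–74.5% |
| 90% | 0.05 × 0.10 = 0.5 points | 0.15 × 0.10 = 1.5 points | 90.5–91.5% |

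At q = 30% the excess would be 15 points for r = 50% and 3 points for r = 90%. Both q and r differ by cut-off: fewer men start below 0.01 than below 0.2 ng/mL, so the excess has to be worked out for each cut-off separately.

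**The case against.** The plan has real safeguards. Naïve status uses all data back to 2006, recorded bilateral orchiectomy is an exclusion, and 365 days of prior activity are required. PSA response also has a baseline-relative form, and an optional testosterone analysis asks for a baseline value. These narrow the gap. They do not close it: none deals with ADT given outside the VA or with low PSA after local treatment, and the optional analysis would accept a castrate baseline.

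The consequence is also limited. Objective 4 is exploratory, depends on sample size, and reports counts and percentages with no comparator. No error rate or primary result is touched. For testosterone, if nearly all men respond, the excess is a point or so. That stands, and it sets the weight of the point.

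A further fair objection is that requiring a baseline testosterone could shrink that analysis badly. That also stands, and is a reason to keep the unrestricted figures.

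A reader might go further and infer that men with low baseline PSA are automatic failures on the percentage-decline endpoints, so that those are biased downwards and need a minimum baseline such as 0.2 ng/mL. The documents do not support this. They state no assay floor, and the lowest nadir cut-off is 0.01 ng/mL. A fall from 0.15 to 0.015 ng/mL is a decline of (0.15 − 0.015)/0.15 = 90%; a fall from 0.05 to 0.025 is 50%. Failure is forced only at or near the floor, and the share of men there is unknown. In the plan 0.2 ng/mL is a nadir cut-off, not a limit of measurability, and using it as an entry condition would discard men who can show a true decline.

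**Conclusion.** The point holds for the absolute-threshold endpoints: testosterone below 50 and 20 ng/dL, and PSA nadir below 0.2, 0.1 and 0.01 ng/mL. As written, each reported percentage exceeds the rate among men who could respond by q(1−r). With q assumed at 5–15%, that is 2.5–7.5 points at r = 50% and 0.5–1.5 points at r = 90%. These are illustrations; they rest on assumed q and r, and on men who start below a cut-off also having an on-treatment value below it. The effect is likely to matter most for the PSA nadirs and to be small for testosterone below 50 ng/dL. It does not extend to the percentage-decline endpoints. It bears on how exploratory percentages are read, and it is cheap to correct before the analysis is run.

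**What to change.** In Table 3 and Section 9.7.4:

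1. For each PSA nadir cut-off, report the proportion among men whose baseline PSA is at or above that cut-off.
2. For each testosterone cut-off, report the proportion among men with a baseline value at or above it, and show men with no baseline value separately.
3. Report the number of ADT-naïve men with baseline testosterone below 50 ng/dL, as a check on the naïve definition, and the number already below each PSA cut-off.
4. Keep the unrestricted figures alongside. In Section 9.9, list ADT given outside the VA as a limitation.

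Leave the percentage-decline endpoints as they are.

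**Cost.** New wording and filters on variables that Table 2 already collects. The downside is smaller denominators, particularly for testosterone, in an analysis that already depends on sample size. The denominator will also differ between cut-offs, so each needs its own count. Misclassified men with no baseline testosterone cannot be identified this way, which is why they should be shown separately. The filters should be fixed before results are seen.
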